10. ANALYSIS OF EFFICACY DATA

All analysis models used for the efficacy endpoints will have their model assumptions checked by evaluating model residuals.

Sample SAS[®] code for the analysis models used are provided in Appendix 1.

All analyses will be based on the FAS unless stated otherwise. The primary comparison for all analyses will be at Week 24.

10.1. PRIMARY ENDPOINT

10.1.1. Primary Estimand

The primary estimand of interest for this study involves a treatment policy strategy. Using this treatment policy strategy, the primary estimand for the primary endpoint is defined as the difference in means between the treatments in the target patient population for the change from baseline at Week 24 in 12MWD, regardless of whether or not the subject continues with treatment or is unable to walk for 12 minutes.

10.1.2. Primary Analysis

Intercurrent events and missing data will be handled using the methodology described in [Section 8.3.1](#). For the primary endpoint the missing values will be imputed using the technique of multiple imputations; this includes incomplete tests considered unrelated to their PMM, which will be set to missing prior to imputation. The multiple imputation step will be performed prior to any imputations for intercurrent events.

Changes from baseline will be analysed using a MMRM. The model will include fixed terms for treatment, visit and the treatment-by-visit interaction. The model will also include the stratification mutation factor and continuous baseline distance walked during the 12MWT as covariates. An unstructured covariance matrix will be used for the repeated visits within a subject and the model will allow the covariance matrix to differ between treatment groups. If this analysis fails to converge, then an analysis of covariance (ANCOVA) will be used which will analyse the change from baseline at Week 24 and at Week 12 separately. The ANCOVA model will include a fixed term for treatment and the mutation stratification factor and continuous baseline distance walked during the 12MWT as covariates. The Kenward-Rogers approximation will be used to estimate the denominator degrees of freedom ([Kenward 1997](#)). The treatment comparison (mavodelpar 100mg - placebo) for the change from baseline at both Week 12 and Week 24 will be estimated. The estimates, standard errors, 95% confidence intervals and associated p-values will be presented for each of the multiple imputation analyses as well as the pooled values.

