8.2.2 Determination of Sample Size

A sample size of 186 subjects (93 per treatment group) provides 90% power, with a two-sided significance level of 5%, of obtaining a statistically significant difference between two treatment groups for the distance walked during the 12MWT. This assumes a treatment effect (difference to placebo in mean change from baseline) size of 60 meters. The standard deviation for the changes from baseline observed in Study REN001-101 was approximately 100 meters. A higher standard deviation, 125 meters, has been assumed for this study due to the longer assessment period (24 weeks instead of 12 weeks) and the larger number of sites included in this study. Allowing for a reduction in power due to subject withdrawals a total of approximately 200 subjects will be randomized.

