3.5. DETERMINATION OF SAMPLE SIZE

A sample size of 186 subjects (93 per treatment group) provides 90% power, with a two-sided significance level of 5%, of obtaining a statistically significant difference between two treatment groups for the distance walked during the 12MWT. This assumes a treatment effect (difference versus placebo in mean change from baseline) size of 60 meters. The standard deviation for the changes from baseline observed in Study [REN001-101](#) was approximately 100 meters. A higher standard deviation, 125 meters, was assumed for this study due to the longer assessment period (24 weeks instead of 12 weeks) and the larger number of sites included in this study. Allowing for a reduction in power due to subject withdrawals, a total of approximately 200 subjects was determined as the appropriate sample size.

The sample size for the DXA sub-study is not based on statistical justification. This sub-study is exploratory in nature and limited to REN001-201 sites that have approval to conduct this sub-study.

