3.6. TREATMENT ASSIGNMENT AND BLINDING

At Screening, all subjects are allocated a unique 6-digit study number by the Integrated Web-based Response System (IWRS), which is used throughout the study. The same subject identifier is used for both REN001-201 and REN001-201-DXA studies. The IWRS uses a computer-generated randomization schedule to assign subjects in a 1:1 allocation ratio to receive either mavodelpar 100 mg or placebo. The randomization is stratified by both mutational genotype (m.3243A>G or other mitochondrial DNA defects) and the screening 12-minute walk distance (≤ 500 meters or > 500 meters).

A subject may be rescreened once with prior Sponsor approval; they will be given a new study number (their original study number will be recorded).

To maintain the blind-blind conditions for the subject and Investigator, study medication is provided as visually matched capsules, and the capsules are supplied in identical bottles.

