In the non-monotone procedure, means and variances from the available data will be used to determine the MCMC starting values; imputed values will be selected with maximum likelihood methods. Initially, 200 MCMC runs will be generated before selecting the first imputed data set. An additional 24 data sets will be generated to reflect the uncertainty due to missing values. The 25 datasets will be separated by 100 iterations of the MCMC. The number of datasets may be increased if the analyses are not found to be sufficiently stable with respect to p-values. Stability will be determined if the p-values are the same to the second decimal place after 3 repetitions. These imputations will be performed separately within each treatment group. The imputation model will include the same covariates as for the analysis model and the value at each scheduled time point. Thus, for the primary endpoint the model will include the stratification mutation factor (in the event of a mis-stratification, the actual value recorded on the database will be used) and the scheduled time points (Screening, Baseline, Week 12 and Week 24). Imputed values will be restricted to being plausible i.e., for the primary endpoint values will be restricted to ≥ 0 meters, and for the secondary endpoint PROMIS T-score will be restricted to ≥ 30.3 and ≤ 83.6 .

In the scenario where a subject has a missing baseline (either not collected or out of window) and the screening value is used as the baseline value, the multiple imputation model will preserve the time the data was collected. So in this scenario the screening value will be present and the baseline value will be missing and imputed. The imputed baseline values will only be used to facilitate the imputation of later visits and will not be used in the analyses. After imputation the imputed baseline values will be replaced with the observed screening value which will be used in the calculation of changes from baseline and analyses (e.g., as a covariate).

The resulting 25 datasets will then be passed through the sequential regression models to impute for monotone missing data. If the non-monotone procedure is not required 25 datasets will be generated from the monotone imputation.

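### The primary model leaves out the continuous screening 12-minute walk distance and uses one baseline slope for both visits, which gives up precision but causes no bias

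*SAP*

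**What the plan says.** SAP 3.6 states: "The randomization is stratified by both mutational genotype (m.3243A>G or other mitochondrial DNA defects) and the screening 12-minute walk distance", with the walk distance cut at 500 m. SAP 4.1 schedules the test at Screening, Baseline, Week 12 and Week 24.

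For the primary analysis, SAP 10.1.2 states: "The model will include fixed terms for treatment, visit and the treatment-by-visit interaction". It continues: "The model will also include the stratification mutation factor and continuous baseline distance walked during the 12MWT as covariates". The ANCOVA, which is the fallback if the MMRM does not converge and otherwise a sensitivity analysis (SAP 10.1.4), has the same two covariates. The Appendix 1 model statement matches the text: mutation, baseline, treatment, visit and treatment-by-visit, with no screening term and no baseline-by-visit term. Protocol 8.5.1 specifies the same covariates.

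The screening walk is used in the imputation model of SAP 8.3.1, whose variables include "the scheduled time points (Screening, Baseline, Week 12 and Week 24"). Neither document gives a reason for using it there and not in the analysis model.

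**The concern.** Genotype, one of the two randomisation factors, is in the model. Screening walk distance is represented only indirectly, through the baseline walk. The two walks are separate measurements taken at least 4 weeks apart. If a single 12MWD carries test-retest error, two pre-treatment walks predict the Week 24 walk better than one, and the residual variance falls.

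The second omission is smaller. Without a baseline-by-visit term, one slope serves both visits. The slopes could differ here, because non-ambulatory subjects and deaths are imputed as 0 m (SAP 8.3.1), which makes their change equal to minus baseline. If such cases accumulate by Week 24, the slope there becomes steeper.

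At stake is the width of the confidence interval for the primary treatment difference, and some power.

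**Working it through.** **Inputs from the documents.** The effect is 60 m: "This assumes a treatment effect (difference versus placebo in mean change from baseline) size of 60 meters" (SAP 3.5). The SD of change is 125 m: "A higher standard deviation, 125 meters, was assumed for this study due to the longer assessment period". The pilot SD was lower: "The standard deviation for the changes from baseline observed in Study REN001-101 was approximately 100 meters" (Protocol 8.2.2). Planned size is 93 per arm, 1:1, two-sided 5%.

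**Inputs assumed.** The documents give no between-visit correlations and no between-patient SD. Each structure below holds the SD of change to Week 24 at 125 m, so the SD of the walk itself is 125/√(2(1−r)), where r is the Baseline to Week 24 correlation. Where timing matters, screening is placed 6 weeks before baseline, inside the allowed 4 to 8 weeks.

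**1. The plan's own figure.** The normal approximation gives n per arm = 2(1.960 + 1.282)² × 125²/60² = 91.2, so 92. The noncentral t gives power 0.8994 at 92 per arm and 0.9025 at 93, so 93 per arm and 186 in total. The stated figure reproduces. It uses the unadjusted SD of change and so does not depend on any covariate.

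**2. Equal correlation r between all visits.** The residual variance share is 1 − r² given baseline, and 1 − 2r²/(1 + r) given baseline and screening. The proportional cut is therefore r²/(1 + r)². Power at 93 per arm is Φ(60/(s√(2/93)) − 1.96), where s is the residual SD.

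| r | SD, baseline only | SD, plus screening | Variance cut | Power |
|---|---|---|---|---|
| 0.6 | 111.8 m | 103.6 m | 14.1% | 95.5% to 97.7% |
| 0.7 | 115.2 m | 105.0 m | 17.0% | 94.4% to 97.4% |
| 0.8 | 118.6 m | 106.2 m | 19.8% | 93.2% to 97.1% |
| 0.9 | 121.8 m | 107.3 m | 22.4% | 91.9% to 96.8% |

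Check at r = 0.8: SD of the walk = 125/√0.4 = 197.6 m; 197.6 × √0.36 = 118.6 m; 197.6 × √0.2889 = 106.2 m. The total N for 90% power falls from 166 to 132. Slopes are equal across visits here, so baseline-by-visit adds 0%.

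**3. Test-retest noise plus drift.** The correlation is reliability × decay^(weeks apart/24).

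| Reliability | 24-week decay | Cut from screening | Cut from baseline-by-visit |
|---|---|---|---|
| 0.95 | 0.85 | 2.5% | 0.72% |
| 0.90 | 0.80 | 3.4% | 0.67% |
| 0.90 | 0.90 | 7.8% | 0.22% |
| 0.90 | 0.95 | 12.6% | 0.06% |
| 0.85 | 0.95 | 13.9% | 0.04% |

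Check of the third row: Screening to Baseline 0.9 × 0.9^0.25 = 0.8766; Baseline to Week 24 0.81; Screening to Week 24 0.9 × 0.9^1.25 = 0.7889. The partial correlation is (0.7889 − 0.8766 × 0.81)/√((1 − 0.8766²)(1 − 0.81²)) ≈ 0.28, and its square is about 0.078.

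**4. Pure Markov decay, 24-week correlation 0.6 to 0.9.** Screening to Week 24 equals the product of the two intermediate correlations, so the partial correlation is zero and screening adds 0%. Baseline-by-visit adds 1.1-2.9%.

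**5. The 500 m stratum alone.** This was simulated with 200 subjects, randomisation stratified at 500 m, truncation at 1000 m at screening, and Week 24 ANCOVA (3,000 runs). At equal correlation 0.8, the empirical SE of the treatment difference is 16.36 m with baseline, 16.22 m with the stratum added, and 15.38 m with continuous screening added. The stratum cuts variance by 1 − (16.22/16.36)² = 1.7%. Continuous screening cuts it by 1 − (15.38/16.36)² = 11.6%. This is less than the residual-variance figure in step 2, partly because stratified randomisation already delivers some of the gain. Each simulated SE has a Monte Carlo error of about 1/√6000 = 1.3%. Under Markov decay at 0.8 neither addition helps (16.84, 16.86 and 16.86 m).

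In the same run at 0.8, the mean model SE with baseline only is 16.66 m against the empirical 16.36 m, so omitting the stratum makes the reported SE slightly conservative.

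**The case against.** The strongest reply is that this is a preference about efficiency. The sample size does not rely on covariates, and power under the SAP model is about 92-96% at the assumed effect for every correlation structure tried. Walk distance is already adjusted for continuously through baseline. All of that stands.

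The size of the gain is also open to challenge. Protocol 3.3 describes the screening test as a familiarisation walk, and eligibility truncates it at 1000 m, so it may not be exchangeable with baseline. An average training effect only shifts the intercept. Training effects that vary between subjects would make screening a noisier predictor and move the gain towards the lower figures. The zero-gain case needs a walk test without measurement error, which is unlikely, but the documents do not exclude small gains.

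On the single slope, the by-visit ANCOVA already frees it, is prespecified, and runs on imputed data. That limb is minor.

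A reader might infer more than the documents support:

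- **Bias, type I error inflation or wrong stated power.** The 186 reproduces, and the simulated SE errs slightly on the conservative side.
- **An established gain of about 20%.** That figure needs equal correlations, for which the documents give no evidence.
- **The 500 m stratum as an adequate fix.** It buys about 2%, and SAP 10.1.5 reports from blinded review that few subjects have a baseline walk of 500 m or less.
- **The same change for the PROMIS T-score model.** No gain was calculated there, and that model already has baseline T-score and baseline 12MWD.

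**Conclusion.** The point holds as lost precision. Both omissions are plain in the SAP text and code. Adding continuous screening 12MWD and baseline-by-visit together reduced Week 24 residual variance in every structure tried, by 1.1% to 22%. Most of that comes from the continuous screening walk: 14-22% under equal correlation, about 2-14% with noise plus drift, 0% under Markov decay. Baseline-by-visit contributes about 0-3%.

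Confidence is high on the omission and on the direction of the effect. It is low on the exact percentage, which rests entirely on correlations that the documents do not give. The change is worth making because the data are already collected and the cost is negligible.

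**What to change.** Before database lock and unblinding:

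- In SAP 10.1.2, in the ANCOVA (fallback and sensitivity) and in the Appendix 1 primary code, add continuous screening 12MWD as a covariate alongside the mutation factor and continuous baseline 12MWD.
- Add a baseline-by-visit term to the MMRM. The by-visit ANCOVA does not need it.
- State how the covariates are set when screening replaces a missing baseline under SAP 8.3.1. Both then take the same value for that subject.
- List the change in SAP Section 14, because the protocol specifies the current covariates.

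The cost is SAP and code wording and about two degrees of freedom in about 200 subjects. No new data are needed.

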10.1.3. Summaries and Plots

Observed, change from baseline and percent change from baseline values will be summarized by visit, both including and excluding imputed values. The imputed summary statistics will be based on Rubin's methodology (Rubin 1987⁵) to combine the means and standard errors from the imputed data sets. The associated 95% confidence intervals for the observed, change from baseline and percent change from baseline means will also be presented.

Mean plots for observed, change from baseline and percent change from baseline values, with 95% confidence intervals, will be presented by treatment group with visit on the x-axis. A reference line for no change (i.e., $y=0$) will be included in the change from baseline and percent change from baseline plots.

Spaghetti plots for the changes from baseline will be plotted over time. The plots will be split by treatment group. The y-axis will be uniform across the plots to allow comparisons. A reference line for no change (i.e., $y=0$) will be included.

A plot of the proportion of subjects achieving no change or an increase in 12MWD at Week 24 will be presented by treatment group. The x-axis will present the change in 12MWD at Week 24 (starting at 0m to maximum change achieved at Week 24) and the y-axis will present the proportion of subjects who achieve this change as a percentage. A corresponding summary table will present proportion of subjects achieving no change or an increase in 12MWD at Week 24 at incremental cut points of 20m. This plot and table will use the average values for subjects across the imputed datasets (including imputations for intercurrent events).

The number of stops and the number of falls will be summarized by visit. If a subject does not walk for the full 12 minutes, then this will be counted as an additional stop when summarizing.

All data will be listed together with changes from baseline, percent change from baseline and assessments imputed due to being at least possibly related to the subject's PMM will be identified. The pre and post exercise measurement for heart rate, blood pressure and RPP scale score will be listed separately, along with their changes from pre-test.

12MWD values, mean, median, minimum and maximum will all be presented to 2 decimal places and SD will be presented to 3 decimal places.

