8.2. GENERAL METHODS

All statistical testing will be at the 5% level of significance (2-sided) and all point estimates for the comparison between treatment groups will be accompanied by 2-sided 95% confidence intervals. To preserve the Type 1 error a fixed sequence testing procedure will be adopted. Testing will be on the FAS. The order of testing for the primary and secondary endpoints will be:

1. Change from Baseline at Week 24 in distance walked during the 12MWT
2. Change from Baseline at Week 24 in the PROMIS T-score

Continuous variables will be summarized using the number of non-missing observations (n), mean, SD, median, minimum, and maximum. Categorical variables will be summarized using counts and percentages.

Unless otherwise specified, the estimated mean and median for a set of values should be displayed to 1 more decimal place than the original values, and SD should be displayed to 2 more decimal places than the original values. The minimum and maximum should be displayed to the same number of decimal places as the original values. Deviations from this convention may arise to take account of the relevance of the precision (e.g., the distance walked in the 12MWT is reported to the nearest cm, but there is no relevance in presenting the mean to the nearest mm). These deviations from convention will be documented in the relevant analysis sections below.

Percentages will be displayed with 1 decimal place; except percentages will not be presented when the count is zero and 100% will be presented as an integer. Unless stated otherwise, percentages of subjects will be based on the number of subjects with non-missing data in the analysis set used for the presentation.

Baseline will be taken as the last available non-missing assessment prior to study drug administration (Day 1). Although the time of completion is not collected for QoL questionnaires (MFIS, PGIS, PROMIS, SF-36, BPI or WPAI:SHP), any completed on Day 1 will be deemed suitable for baseline as the questionnaires are requested in the protocol to

be completed prior to dosing and, even if after dosing, there is no anticipated effect after a single dose.

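### The Week 24 12MWD responder plot and table apply the cut points to each subject's averaged imputations, which biases the displayed proportions; they should be computed within each imputed dataset and then averaged

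*SAP*

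**What the plan says.** SAP section 10.1.3 plans a by-arm plot of the proportion of subjects with no change or a gain in 12MWD at Week 24. Its x-axis is described as "starting at 0m to maximum change achieved at Week 24". A matching table steps through the same scale every 20 m. For both, the rule is: "This plot and table will use the average values for subjects across the imputed datasets (including imputations for intercurrent events".

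Other imputed results are handled differently. Section 10.1.3 pools the imputed means and standard errors by Rubin's method. Section 8.3.1 analyses each of the 25 imputed datasets and then combines the results.

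Section 8.3.1 also decides which values are imputed, and how:
- Gaps clearly unrelated to PMM or study treatment are treated as MAR and multiply imputed, separately by arm.
- Withdrawals, and ambulatory subjects unwilling or prevented, for possibly related reasons get worst-case random draws.
- Deaths and non-ambulatory subjects are set to 0 m.

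**The concern.** Whether a subject reaches a threshold is a non-linear function of the change in distance. The proportion of averaged values above a cut is therefore not the average of the proportions above it. Averaging 25 draws removes most of the imputation spread. A MAR-imputed subject becomes a near-certain responder below the conditional mean and a near-certain non-responder above it. The uncertainty that multiple imputation exists to carry is lost from this output, and the SAP gives no reason for treating it differently.

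This is the only threshold-type display of the primary endpoint in section 10.1, and readers will use it to judge individual benefit. At cuts between the two arm means, the rule raises the higher arm and lowers the other, so the displayed difference is too large there.

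**Working it through.** **The plan's own figure.** The SAP gives no figure for this display, but its sample-size inputs supply the scale. Section 3.5 says "This assumes a treatment effect (difference versus placebo in mean change from baseline) size of 60 meters" and "A higher standard deviation, 125 meters, was assumed for this study". With two-sided alpha 5%, 90% power and 1:1 allocation, the normal formula 2 × (1.960 + 1.282)² × 125² / 60² gives 91.2, so 92 per arm. The two-sample t calculation gives 93 per arm (power 90.25% at 93, 89.94% at 92). The stated 186 is reproduced.

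**Assumptions not in the documents.** Arm means are 60 and 0 m. The MAR-missing share is 3.5%, 7% or 15% in each arm. The 7% is the whole allowance implied by "a total of approximately 200 subjects was determined as the appropriate sample size" against 186 evaluable: 1 − 186/200 = 7%.

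**Closed form, no Week 12 walk, covariates ignored.** One draw has SD 125 m. The average of 25 independent draws has SD 125/√25 = 25 m. For an arm with mean μ and cut c:

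bias = missing share × [P(average ≥ c) − P(one draw ≥ c)]

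At c = 40 m and 7% missing:
- Active: 0.07 × (0.788 − 0.564) = +1.6 points.
- Placebo: 0.07 × (0.055 − 0.374) = −2.2 points.
- The gap goes from about 18.9 to 22.7 points, a widening of 3.8.

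Across cuts, at 7% missing:

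| Cut (m) | Active: draw / average | Placebo: draw / average | Change in gap (points) |
|---|---|---|---|
| 0 | 68.4% / 99.2% | 50.0% / 50.0% | +2.2 |
| 20 | 62.6% / 94.5% | 43.6% / 21.2% | +3.8 |
| 40 | 56.4% / 78.8% | 37.4% / 5.5% | +3.8 |
| 100 | 37.4% / 5.5% | 21.2% / 0.0% | −0.8 |
| 120 | 31.6% / 0.8% | 16.9% / 0.0% | −1.0 |

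The bias is proportional to the missing share. At +40 m it is +1.9 points for 3.5% and +8.2 for 15%.

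**Simulation with regression imputation.** This used 25 imputations by arm, 100 subjects per arm and 400 replicates. Further assumptions were a Week 12–Week 24 correlation of 0.7 and a baseline of mean 650 m, SD 180 m.
- No post-baseline walk, 20 m cut, 7% missing: the SAP rule gives 64.4% v 42.4% (gap 22.0). Cutting within each dataset gives 62.5% v 43.6% (gap 18.9). Complete data give a gap of 19.1.
- The same at 15% missing: gap 25.6 under the SAP rule, 18.8 when cut within datasets.
- The widening is therefore 3.1 and 6.8 points, somewhat below the closed form, as expected when the imputation parameters are estimated.
- Week 12 observed for the missing subjects: widening of at most about 0.6 points at 7% and 1.2 points at 15%.
- Cutting within each dataset matched the complete-data proportions to within about 0.3 points.

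**Other arm means.** With 94 v 34 m (the pilot's 94 m gain, less 60 m for placebo) and no Week 12 walk, the closed form widens the gap at 60 m by 4.0 points at 7% missing. At 0 m it narrows slightly (0.3 to 1.2 points over the three missing shares).

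**Worst-case draws.** If the worst observed change were −300 m, 0.8% of draws and 0% of averages would reach 0 m; at −200 m, 5.5% and 0%. Values fixed at 0 m are the same in every dataset, so averaging does not alter them.

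**The case against.** The strongest reply is that this is a descriptive display with no p-value or interval, outside the testing sequence, and that few subjects would be affected. SAP section 8.3.1 reserves MAR for clearly unrelated reasons and asks subjects who stop drug to return for the walk. Section 8.4 lets an early-termination walk on Days 147–189 count as Week 24. The MAR examples (site unable to test, injury, fire alarm) are largely single-visit events, so a Week 12 walk would often exist. The imputation model also conditions on mutation, screening, baseline and Week 12, so averages sit near each subject's own conditional mean rather than the arm mean. Even the 3.8-point case is about half the sampling standard error of the gap: √[(0.564 × 0.436 + 0.374 × 0.626)/100] = 6.9 points.

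All of this stands as a limit on size. None of it makes the rule correct: the bias is systematic and avoidable.

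A reader might also infer that the plot conceals all worsening because it starts at 0 m. It does not: 100% minus the height at 0 m is the share who worsened, and section 10.1.3 also plans spaghetti plots with a zero line and reports minima. What this plot omits is the size of the declines.

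**Conclusion.** The averaging rule biases the displayed responder proportions wherever Week 24 values are MAR-imputed. That follows from the rule itself. The size rests on an unstated missing share and on whether Week 12 was observed: from about half a point to about 4 points on the gap at 7% missing, for cuts between the arm means.

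A reader might infer that the display always favours the drug. The documents do not support that: the direction depends on where the cut lies relative to the arm means, and the gap narrows at high cuts. Nor does the point reach the primary result. The primary estimand is a difference in means, analysed within each dataset and pooled, so its test, alpha and power are unchanged. Subjects given worst-case or 0 m values are hardly affected. This is a correction to a descriptive output.

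**What to change.** In SAP section 10.1.3, replace the averaging sentence: compute the proportion at each cut point within each of the 25 imputed datasets, intercurrent-event imputations included, and average over datasets, with Rubin's rules if an interval is shown. The cost is a few lines of code and a wording change before database lock. The one small drawback is that pooled counts in the table will not be whole numbers; a footnote can explain this.

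Optionally, extend the x-axis below 0 m to show the full cumulative distribution, so that the size of any worsening can be compared between arms. This is a display preference, not the correction of an error.
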